#### **4.5.2.2. COVID-19 Assessment and COVID-19 AEs**

A standardized MedDRA Query (SMQ) will be used to identify all COVID-19 AEs.

The overall incidence of AEs and SAEs of COVID-19, COVID-19 AEs leading to study intervention discontinuation, COVID-19 AEs leading to study withdrawal, and Grade 3 and 4 COVID-19 AEs / severe COVID-19 AEs will be summarized. The incidence of these events at individual PT level can be obtained from the standard AE/SAE summaries.

COVID-19 assessments for participants with COVID-19 AEs will be summarized.

If >5% participants report  $\geq 1$  COVID-19 AE, then onset and duration of the first occurrence of COVID-19 AEs, and COVID-19 AE symptoms (from the COVID-19 eCRF page) will be summarized. The same rule will apply to COVID-19 SAEs.

#### **4.5.2.3. Impact of COVID-19 Pandemic on Safety Results**

The impact of the COVID-19 pandemic on the safety results will be assessed. Pandemic measures began in different countries at different times. A dataset containing the date when pandemic measures began, as determined by the GSK country Issue Management Teams (IMT), will be used to determine the start date of each wave of pandemic measures within each country.

Summaries of the incidence rates of AEs, Common AEs, SAEs and Grade 3 and 4 AEs / severe AEs, before (AE onset date < pandemic measure start date) and after (AE onset date  $\geq$  pandemic measure start date) the start of the COVID-19 pandemic will be produced, overall and by country/region, gender and age group (<18, 18-64,  $\geq$ 65).

#### **4.5.3. Additional Safety Assessments**

##### **4.5.3.1. Laboratory Data**

Only central lab data will be used for summary analyses and figures; local lab data will be included in listings, as appropriate.

Summary statistics for changes from baseline for each numeric parameter at each visit will be presented, separately for all clinical chemistry parameters, all hematology parameters and all urinalysis parameters.

For immunology parameters, summary statistics for actual value and change from baseline data for each parameter at each visit will be presented, separately for all numeric parameters. Listings will also be created.

For categorical immunology parameters c-ANCA and p-ANCA, summary table of baseline Negative to post-baseline Positive, baseline value no change, and baseline Positive to post-baseline Negative will be created. Listing will be created as well.

For coagulation parameters Prothrombin Intl. Normalized Ratio (INR), Prothrombin Time (PT) and Activated Partial Thromboplastin Time (aPTT), summary statistics for actual at each visit will be presented. Listing will be created as well.

Shift tables for laboratory parameters showing baseline toxicity versus maximum post-baseline (on-treatment and off-treatment periods combined) toxicity for each grade (Grade 1, Grade 2, etc.) for chemistry and hematology parameters will be provided.

Increase to Grade 3 or higher lab abnormalities for platelets, ALT, AST, INR, total bilirubin, serum creatinine, eGFR, ACR will be summarized.

Laboratory values outside of normal range will be summarized and listed.

Grading categories for laboratory tests are determined using the DAIDS grading system Version 2.1 [[National Institute of Allergy and Infectious Diseases. Division of AIDS, 2017](#)].

Summary of post-baseline hepatobiliary laboratory abnormalities will be provided based on both planned and unplanned assessments (e.g. unscheduled visit, monitoring event).

Liver monitoring and stopping event reporting will be summarized and listed. The Liver monitoring and stopping criteria are described in the protocol Section 7.1.1.

The worst-case urinalysis results post-baseline (on-treatment and off-treatment periods combined) relative to baseline will be summarized.

Potential Drug induced vascular injury and complement monitoring/stopping event will be summarized and listed based on laboratory parameters (C3, C4, Bb, C5a, hs-CRP, MCP-1, p-ANCA, c-ANCA, eGFR, Bilirubin, and platelet count). The Drug Induced Vascular Injury and Complement monitoring and hold or stopping criteria are described in the protocol Section 7.1.2.

Haematological monitoring/stopping event will be summarized and listed based on laboratory parameters (platelet count and anti-platelet antibodies). The haematological monitoring and stopping criteria are described in the protocol Section 7.1.3.

Potential Drug induced kidney injury (renal) monitoring and hold or stopping events will be identified programmatically and will be summarized and listed based on laboratory parameters (ACR, Urinalysis RBC, serum creatinine, and eGFR). The kidney injury monitoring and stopping criteria are described in the protocol Section 7.1.4.

Hold/stopping event profile will be provided for any subject who has met hold or stopping criteria specified in protocol Section 7.1. Relevant information will be reported, including baseline characteristics, AEs/SAEs, concomitant medication, medical history/current medical conditions, study treatment administration details, laboratory values, and individual line plots of complement (C3/C4/C5a/Bb), inflammatory markers (hs-CRP/MCP-1), serum creatinine/creatinine clearance or eGFR/ACR, and platelet count.

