7.1.2. Drug Induced Vascular Inflammation and Complement Stopping Criteria

If any of the following are observed, results should be confirmed with a repeat sample collection and analysis, and if confirmed, further evaluation for alternative causes should be pursued in consultation with the Medical Monitor.

Repeat sample collection of C3, C4, Bb, C5a would be triggered by changes in the clinical signs and symptoms of complement activation ($\geq 2+$ haematuria; increasing urine ACR; vasculitic or purpuric rash; peripheral neuropathy; jaundice). Additional complement analyses for example CH50, Factor B level, Factor H level, sC5b-9 should also be considered in discussion with the Medical Monitor and Safety Panels.

1. **Persisting & deteriorating longitudinal trends in change from baseline for C3 and/or C4 defined as:**
 - a. If participant's baseline C3 and/or C4 is **within** the lab's normal range at baseline: there is a sequential decline in C3 and/or C4 once levels have fallen below the lower limit of normal (LLN) for ≥ 4 weeks OR
 - b. If participant's baseline C3 and/or C4 is **below** the lab's LLN at baseline: there is further sequential decline in C3 and/or C4 for ≥ 4 weeks OR
 - c. Regardless of baseline C3 and/or C4 level: there is a **$\geq 80\%$ reduction** in the participant's C3 and/or C4 level at any point
AND
 - d. There is an associated **≥ 3 -fold increase** in Bb and/or C5a from participant's baseline OR

- e. There are associated biochemical sequelae for example, a rising high sensitivity C-reactive protein (hs-CRP); rising monocyte chemoattractant protein (MCP-1); new thrombocytopenia, new renal impairment with no other explanation such as intercurrent infection OR
- f. There are associated clinical sequelae, for example, $\geq 2+$ haematuria; increasing urine ACR; vasculitic or purpuric rash; peripheral neuropathy; jaundice OR
- g. There is new cANCA or pANCA positivity

2. Persisting & deteriorating longitudinal trends in change from baseline for Bb and/or C5a where

- a. There is a ≥ 3 -fold increase in Bb and/or C5a over baseline AND
- b. This is persisting or increasing week on week in sequential data plots OR
- c. There are associated biochemical sequelae for example, a rising hs-CRP; rising MCP-1, new thrombocytopenia, new renal impairment with no other explanation such as intercurrent infection OR

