- d. There are associated clinical sequelae, for example, $\geq 2+$ haematuria; increasing urine ACR, vasculitic or purpuric rash; peripheral neuropathy; jaundice or any combination of these OR
- e. There is new cANCA or pANCA positivity

Treatment Hold/Treatment Discontinuation

- Hold study treatment during evaluation of alternative causes for decreased C3 and/or C4 associated with increased inflammatory markers including one or more of hs-CRP, MCP-1, Bb and C5a
- Discontinue study treatment permanently if persistent change from baseline (≥ 4 weeks) in biomarker pattern (decreased C3/C4 associated with increased inflammatory markers including one or more of hs-CRP, MCP-1, Bb, C5a) without clear alternative explanation.
- Discontinue study treatment permanently if suspect clinical sequelae of complement activation, drug induced vascular inflammation, vasculitis or auto-immunity regardless of biomarkers changes or persistence.

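### The SAP's laboratory list for potential vascular injury/complement events omits urine ACR and urinalysis blood, so events completed only by those signs under protocol 7.1.2 (most clearly item 1f) would not be identified

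*SAP*

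**What the plan says.** SAP 4.5.3.1 (Laboratory Data) states that potential drug-induced vascular injury and complement monitoring/stopping events will be "summarized and listed based on laboratory parameters (C3, C4, Bb, C5a, hs-CRP, MCP-1, p-ANCA, c-ANCA, eGFR, Bilirubin, and platelet count"). It then gives the source of the rules: "The Drug Induced Vascular Injury and Complement monitoring and hold or stopping criteria are described in the protocol Section 7.1.2".

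In protocol 7.1.2, criterion 1 needs a qualifying fall in C3 and/or C4 (items 1a to 1c) together with one of items 1d to 1g. Item 1f is associated clinical sequelae. Its examples begin with haematuria of 2+ or more and continue "increasing urine ACR; vasculitic or purpuric rash; peripheral neuropathy; jaundice OR" the next item. Criterion 2 starts from a 3-fold or greater rise in Bb and/or C5a. Item 2d gives the same examples: haematuria of 2+ or more, then "increasing urine ACR, vasculitic or purpuric rash; peripheral neuropathy; jaundice or any combination of these OR" the next item. The same signs prompt resampling: "Repeat sample collection of C3, C4, Bb, C5a would be triggered by changes in the clinical signs and symptoms of complement activation".

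The SAP does use urine ACR and urine red cells in the same section, but only for renal events under protocol 7.1.4, which rest on "laboratory parameters (ACR, Urinalysis RBC, serum creatinine, and eGFR").

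**The concern.** The SAP cites the criteria of 7.1.2 but names inputs that cannot reproduce them in full. It does not look like a deliberate split between laboratory and clinical criteria. Bilirubin is on the list, and its evident role is to stand in for jaundice, which sits in the same items 1f and 2d. So one sign from those items gets a laboratory proxy, while the two that are themselves laboratory results are left out. SAP Table 1 (changes to protocol-defined analyses) does not mention the omission.

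The stake is the completeness of one safety display. Vascular inflammation and complement activation is an adverse event of special interest (protocol 8.2.9.2, SAP 4.5.2.1). Protocol 8.2.9.4 attributes glomerulonephritis seen with this drug class to a proinflammatory effect, so urinary signs are a natural way for such an event to appear. A display that cannot see them may show fewer participants meeting the criteria than the protocol's wording would.

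**Working it through.** The check is a comparison of passages; the plan gives no figure to reproduce.

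**Step 1. Match each qualifier in protocol 7.1.2 to the SAP list.** Bb and C5a, and cANCA and pANCA, are counted separately.

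| Qualifier | Items | SAP list parameter |
|---|---|---|
| Bb, 3-fold or greater | 1d, 2a | Bb |
| C5a, 3-fold or greater | 1d, 2a | C5a |
| Rising hs-CRP | 1e, 2c | hs-CRP |
| Rising MCP-1 | 1e, 2c | MCP-1 |
| New thrombocytopenia | 1e, 2c | platelet count |
| New renal impairment | 1e, 2c | eGFR |
| Haematuria, 2+ or more | 1f, 2d | **none** |
| Increasing urine ACR | 1f, 2d | **none** |
| Jaundice | 1f, 2d | bilirubin (proxy) |
| Vasculitic or purpuric rash | 1f, 2d | not a laboratory test |
| Peripheral neuropathy | 1f, 2d | not a laboratory test |
| New cANCA positivity | 1g, 2e | c-ANCA |
| New pANCA positivity | 1g, 2e | p-ANCA |

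There are 13 qualifiers. Removing rash and neuropathy leaves 13 − 2 = 11 that a laboratory can measure. The list covers 9, so 11 − 9 = 2 are missing. The list's remaining two parameters, C3 and C4, are the entry conditions of criterion 1.

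**Step 2. Check the action rules at the end of 7.1.2.** The hold rule and the persistent-biomarker discontinuation rule use C3/C4 with hs-CRP, MCP-1, Bb or C5a. All 6 markers are listed, so neither rule is affected. The third rule is "Discontinue study treatment permanently if suspect clinical sequelae of complement activation, drug induced vascular inflammation, vasculitis or auto-immunity regardless of biomarkers changes or persistence". It rests on clinical suspicion, which no laboratory list can fully derive.

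**Step 3. Isolate the missed case.** Take a participant whose C3 starts in the normal range, falls below the lower limit of normal and declines sequentially for at least 4 weeks (item 1a). New 2+ haematuria appears (item 1f). Bb and C5a stay below 3-fold, hs-CRP and MCP-1 do not rise, platelets, eGFR and bilirubin are normal, and ANCA is negative. Criterion 1 is met as 1a plus 1f. The SAP list sees the C3 decline but none of the signs that complete the criterion.

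**Step 4. Check that the data exist.** In the Schedule of Activities, complement is sampled after Day 1 on Days 15, 29, 50, 57 and 71, then from Day 92 at every scheduled follow-up visit to Day 246. Urinalysis and urine ACR are scheduled at each of these visits.

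**Step 5. Check whether the renal display recovers the case.** Protocol 7.1.4 calls for evaluation at a persistent ACR of 30 mg/g or more, or at 5 or more red cells per high power field. Protocol 7.1.2 refers to an increase in ACR and to 2+ haematuria. The thresholds differ, and the renal display has no link to complement.

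**The case against.** Several parts of the opposing case stand.

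- **Holds and renal impairment.** A reader might infer that hold events are missed, or that every event qualifying through the kidney is lost. The documents support neither. The hold rule uses only listed markers, and eGFR covers the qualifier that 7.1.2 words as "new thrombocytopenia, new renal impairment with no other explanation such as intercurrent infection OR" the next item.
- **Criterion 2.** A reader might take a single, non-persisting 3-fold Bb rise with haematuria as a clear missed event. It is not clear. The criterion is headed as a persisting and deteriorating trend, and its mix of AND and OR can be read in more than one way. If the rise does persist, item 2b is met from Bb or C5a alone, and both are listed. Item 2d matters only if it counts as an alternative to persistence. Criterion 1f is therefore the firmer ground.
- **Narrowness under criterion 1.** Rising hs-CRP and MCP-1 have no threshold in items 1e and 2c, so many participants with haematuria or rising ACR may qualify by another route.
- **Nature of the display.** The SAP calls these potential events, and only for renal events does it say that they are identified programmatically. Further detail may sit in the Output and Programming Specification, which is not among the documents. Criteria 1 and 2 lead first to repeat sampling and evaluation, so this display does not itself protect participants.
- **Other outputs.** Worst-case urinalysis, increases to Grade 3 or higher in ACR, renal events and adverse events of special interest are all reported. Profiles are promised for anyone who met Section 7.1 hold or stopping criteria, but they help here only if the participant has been identified as meeting them.

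None of this explains why bilirubin is listed for items 1f and 2d while ACR and urinalysis blood are not.

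**Conclusion.** The SAP text is wrong as written: its list does not carry two laboratory-measured qualifiers that the cited protocol section names. Coverage is 9 of 11. Events completed only by haematuria or increasing ACR, most clearly under item 1f, would not be identified in this table and listing.

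The effect is under-identification in one descriptive safety display. A reader might infer that safety data are lost or that participants are less protected. The documents do not support that, because the results are collected, are reported elsewhere and are acted on through protocol 7.1.2 during the trial.

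The number of participants affected cannot be estimated. The documents give no rate, and protocol 2.3.1 says that vascular inflammation has not been seen in clinical studies of this drug to date. As illustration only, one missed participant is 1/20 = 5 percentage points at the planned size, or 1/24 = 4.2 points at the maximum.

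The conclusion assumes that the SAP list is the full input to the derivation. If the programming specification already adds the two parameters, only the SAP text needs correcting.

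**What to change.** In SAP 4.5.3.1, for vascular injury and complement monitoring/stopping events:

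- Add urine ACR and urinalysis blood to the parameter list.
- Flag them at the same visits as the complement change, so that the link in items 1f and 2d is kept.
- Define them in the terms of protocol 7.1.2: haematuria of 2+ or more, and an increase in ACR from baseline, with the programming definition of an increase written out. The 7.1.4 renal thresholds should not be reused, because they would not apply 1f and 2d as worded.
- State that rash and peripheral neuropathy are taken from AE or clinical data.
- State how the AND/OR structure of criterion 2 is programmed, once the study team has confirmed the intended reading.

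Coverage of the laboratory-measurable qualifiers becomes 11 of 11. The cost is a short text change, one agreed ACR definition and a small programming change. No new data are needed.

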#### **4.5.3.2. Vital Signs**

Summaries of grade increase in temperature, systolic blood pressure (SBP) and diastolic blood pressure (DBP) will be provided separately. These summaries will display the number and percentage of participants with any grade increase, increase to Grade 2, increase to Grade 3 and increase to Grade 4 (for temperature only), for worst case post-baseline only. The grade definition for temperature is: Grade 1 ( $38.0^{\circ}\text{C} - < 38.6^{\circ}\text{C}$ ), Grade 2 ( $\geq 38.6^{\circ}\text{C} - < 39.3^{\circ}\text{C}$ ), Grade 3 ( $\geq 39.3^{\circ}\text{C} - < 40.0^{\circ}\text{C}$ ), Grade 4 ( $\geq 40.0^{\circ}\text{C}$ ). The grade definition for SBP is: Grade 1 (140-159), Grade 2 (160-179), Grade 3 ( $\geq 180$ ). The grade definition for DBP is: Grade 1 (90-99), Grade 2 (100-109), Grade 3 ( $\geq 110$ ). The summaries will be produced for worst case post baseline only.

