8.2.3. Vital Signs

Temperature, pulse rate, respiratory rate, and blood pressure will be assessed.

Blood pressure and pulse measurements will be assessed with a completely automated device. Manual techniques will be used only if an automated device is not available.

Blood pressure and pulse measurements should be preceded by at least 5 minutes of rest for the participant in a quiet setting without distractions (e.g., television, cell phones).

Vital signs will be measured after 5 minutes rest and will include temperature, systolic and diastolic blood pressure, and pulse and respiratory rate.

If assessments are scheduled for the same nominal time, then 12-lead ECG and vital signs must be completed prior to blood collection. The order of conducting the 12-lead ECG and vital sign measurements is flexible but should allow the blood collection to occur at the exact nominal time.

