9.4.5. Safety Endpoints

All safety analyses will be based on the Safety Population.

Exposure to study medication, measured by the number of injections and percent of planned number of injections of study drug, will be summarized.

[figure not shown]
The percent of participants reporting adverse events (AEs) will be tabulated. The following summaries of AEs will be provided:

- Incidence and severity of All AEs;
- Incidence and severity of treatment related AEs;
- Incidence and severity of AEs leading to withdrawal from study;
- Incidence of serious AEs (SAEs).

Laboratory data and vital signs (absolute values and change from baseline) will be summarized by visit. In addition, the maximum post-baseline toxicity grade (based on DAIDS categories) will be tabulated.

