## 4.8. Changes to Protocol Defined Analyses

Changes from the originally planned statistical analysis specified in the protocol are detailed in [Table 1](#).

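### SAP 4.5.3.2 does not carry out the by-visit vital-sign summaries stated in protocol 9.4.5, and the SAP does not declare the difference

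*SAP*

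**What the plan says.** The protocol's commitment is in section 9.4.5: "Laboratory data and vital signs (absolute values and change from baseline) will be summarized by visit". Its next sentence adds a tabulation of maximum post-baseline toxicity grade, so grading supplements the by-visit summaries and does not replace them. Protocol 8.2.3 lists what is measured: "Temperature, pulse rate, respiratory rate, and blood pressure will be assessed". The safety endpoint in protocol section 3, repeated in SAP 1.1, names vital signs.

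SAP 4.5.3.2 covers vital signs in one paragraph: "Summaries of grade increase in temperature, systolic blood pressure (SBP) and diastolic blood pressure (DBP) will be provided separately". It ends: "The summaries will be produced for worst case post baseline only". The blood pressure grades begin at hypertensive levels: "The grade definition for SBP is: Grade 1 (140-159), Grade 2 (160-179), Grade 3" at 180 or more. DBP is graded from 90 and temperature from 38.0 °C.

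For laboratory data, SAP 4.5.3.1 keeps by-visit tables. For chemistry, haematology and urinalysis: "Summary statistics for changes from baseline for each numeric parameter at each visit will be presented". For coagulation: "summary statistics for actual at each visit will be presented". Immunology parameters get both actual value and change.

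SAP 4.8 is the place for departures: "Changes from the originally planned statistical analysis specified in the protocol are detailed in" Table 1. That table has one entry, on time to maximum ALT.

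**The concern.** Vital signs are a named part of the safety endpoint, and the protocol says how they will be summarised. A programmer working from SAP 4.5.3.2 would produce three worst-case grade tables and nothing else. Pulse and respiratory rate would be collected throughout and not tabulated. Movement in blood pressure would be visible only if it crossed an upward grade boundary.

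With one arm and about 20 participants, within-participant change described over visits is the main way to see a vital-sign effect. A worst-case count cannot show when a change occurred, whether it persisted, or whether it reversed after the last dose. Falls in blood pressure and changes in pulse are of some interest here: the protocol plans five liver aspirates per participant and lists thrombocytopenia leading to bleeding among the risks.

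**Working it through.** No sample size, rate or probability is involved, so the check is a comparison of the two documents plus a count.

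**Step 1: measures collected.** Protocol 8.2.3 gives temperature, pulse, respiratory rate and blood pressure. Counting systolic and diastolic separately makes five.

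**Step 2: scheduled assessments.** From the Schedule of Activities, excluding screening and early termination:
- Table 2, baseline to Day 50: 11
- Table 3, Day 57 to Day 78: 4
- Table 4, Day 85 to Day 246: 8
- Total: 11 + 4 + 8 = 23

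**Step 3: what each document specifies.**

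| Measure | Protocol 9.4.5: value and change by visit | SAP: value and change by visit | SAP: worst-case upward grade |
|---|---|---|---|
| Temperature | yes | not specified | yes |
| SBP | yes | not specified | yes |
| DBP | yes | not specified | yes |
| Pulse | yes | not specified | no |
| Respiratory rate | yes | not specified | no |

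By-visit coverage is 5 of 5 in the protocol and 0 of 5 in the SAP. Worst-case grade coverage in the SAP is 3 of 5. Pulse and respiratory rate are not named anywhere in the SAP text available.

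**Step 4: what the grade tables can detect.** SBP below 140, DBP below 90 and temperature below 38.0 °C carry no grade. A fall from any baseline can only leave the grade unchanged or lower it, so it is never a grade increase. A rise that stays below the first boundary, or within one grade, is not counted either.

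**Step 5: is the change declared?** SAP Table 1 lists only the replacement of one time-to-maximum-ALT table by four. Vital signs are not there.

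**Step 6: laboratory data against the same protocol sentence.**
- Chemistry, haematology, urinalysis: change by visit is specified; actual value by visit is not.
- Coagulation: actual value by visit is specified; change is not.
- Immunology: both are specified.

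One half of the promised pair is missing for the first two groups, but each still has a by-visit table.

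**The case against.** The strongest reply is that SAP 4.5.3.2 does not exclude by-visit tables. Its restriction to the worst case describes the grade-increase summaries and can be read as limited to them. Elsewhere the SAP looks prepared for by-visit output: 6.2.4 maps early-termination data to visit windows for numeric laboratory and vital-sign parameters, 6.2.6 refers to by-visit summary tables and to summaries of observed values, and 4.1.1 sets a default format for continuous data. A worst-case table needs no visit mapping. The SAP also leaves output detail to an Output and Programming Specification that is not among the documents. If by-visit tables were always intended, Table 1 had nothing to declare.

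Much of this stands as evidence about intent. A reader might infer that the sponsor deliberately dropped the analysis, and the documents do not support that. None of these places schedules a vital-sign table, however. They give windows, a format and rules for tables specified elsewhere, and 4.5.3.2 is where such tables should be specified.

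Two other strong readings also fail. A reader might infer that these changes would appear in no safety output at all. Under protocol 10.3.1, a vital-sign abnormality the investigator judges clinically significant is an adverse event, and SAP 4.5.2 would tabulate it. A reader might also infer that laboratory trends are hidden, ALT and platelets included. Both have by-visit change, toxicity shift tables, Grade 3 or higher summaries and stopping-event summaries. ALT additionally has the proportion above 3 times ULN over time, AUC and time-to-peak analyses.

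Finally, no adverse event of special interest and no stopping rule is defined by pulse, respiratory rate or blood pressure, which limits the consequence.

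**Conclusion.** The protocol and SAP conflict on vital signs, and the conflict is undeclared. As written, the SAP specifies the promised by-visit summary for none of five measures, and no vital-sign table at all for pulse, respiratory rate or falls in blood pressure. This is more than missing detail, because following the SAP literally leaves part of a named safety endpoint without its stated analysis.

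Severity is minor. The primary estimand and the 50% posterior criterion are unaffected, clinically significant changes would still reach the adverse event tables, and no missed signal has been shown. The laboratory difference is an alignment matter only.

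The conclusion rests on the SAP text supplied. If the output specification already lists by-visit vital-sign tables, the remedy reduces to correcting the SAP wording to match.

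**What to change.** 1. In SAP 4.5.3.2, add by-visit descriptive summaries (n, mean, SD, median, minimum, maximum, the SAP 4.1.1 default) of actual value and change from baseline for temperature, pulse, respiratory rate, SBP and DBP. Keep the grade-increase tables.
2. Failing that, enter the reduction in SAP 4.8 Table 1 with a reason.
3. As a minor alignment with protocol 9.4.5, add to SAP 4.5.3.1 actual values by visit for chemistry, haematology and numeric urinalysis, and change from baseline for coagulation.

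The cost is a short SAP edit and a few standard tables. The data are already collected, and the baseline definition (SAP 4.1.2) and early-termination windows (SAP 6.2.4) already exist, so no new assessment or derivation rule is needed.
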